6.2.1 Other Institutions and Physicians

This clinical study is not transferable to other institutions attended by the investigator unless prior approval is obtained from both BIOTRONIK and the appropriate IRB. However, there are certain situations where an investigator might not be immediately available to provide the necessary medical care for a subject enrolled in the clinical study (such as a subject emergency room visit for medical treatment). In these instances a protocol deviation will not be issued and all available data will be utilized. In any such situations, the IRB and the investigator must continue to provide oversight for that patient's medical care and rights as a research subject.

6.3 Informed Consent

All subjects must sign and date an IRB approved Informed Consent Form (ICF) prior to enrollment or any protocol related procedures. Legally authorized representatives are not allowed to consent on a subject's behalf. Informed consent should be obtained in accordance with the FDA regulations (21CFR, Part 50), ICH/GCP Guidelines, the Declaration of Helsinki and any other national or local requirements. The consent process, including discussion of the study, should be documented within the subject's medical record. A copy of the completed (signed) informed consent form should be given to the subject.

This study does not include vulnerable patient populations. The investigator is required to inform BIOTRONIK and the reviewing IRB within 5 days if any subject was not appropriately consented to participate in the study.

7 Data Collection

7.1 Electronic Data Capture (EDC)

MedNet Solutions, Inc. is a privately held company that specializes in web-based clinical data management technology. MedNet will host the EDC system and provide a secure environment that is accessible to authorized individuals through the internet. BIOTRONIK will implement a study specific configuration using this software to meet the data collection requirements of the protocol. The EDC system is 21 CFR Part 11 compliant and is the platform for eCRF data entry, clinical data discrepancy resolution, and access to reports for BIOTRONIK, specified study sites, and any other parties authorized by BIOTRONIK.

7.2 Electronic Case Report Forms (eCRFs)

Original data will be collected from each study site and recorded into the EDC system, audited and monitored by BIOTRONIK, via completion of eCRFs. The investigator will be required to use an electronic signature to approve the content of the data reported in the eCRFs.

The iMedNet EDC system incorporates the ability for sites to upload subjects' signed and dated ICFs for the purposes of remote review of signed ICFs by Centralized Monitors to help identify any potential ICF compliance concerns early in the study prior to an on-site monitoring visit. As BIOTRONIK utilizes risk-based monitoring, the ability to upload unredacted informed consent forms is one of the factors taken into account when determining the need for a monitoring visit. An unredacted version of the subject's signed and dated ICF allows the Centralized Monitor to verify that the ICF was signed and dated by the subject prior to study procedures being conducted and that the subject signature and date are legible, complete, and correlate with the subject initials entered into EDC.

iMedNet is compliant with 21 CFR Part 11 Electronic Records; Electronic signatures. MedNet systems utilize industry standard methods for maintaining confidentiality and integrity of client data, and include (but are not limited to) SSL encryption, digital signatures, and secure technology policies and procedures. If additional information is required, iMedNet's Traceability Matrix illustrating evidence of iMedNet's compliance with all 21 CFR Part 11 requirements can be provided upon request.

If a site is not allowed to upload unredacted subject ICFs to the EDC system based on institutional policies, the site must provide to BIOTRONIK either a copy of the IRB or institutional policy or if a formal policy does not exist, a Note to File documenting this policy signed and dated by the Principal Investigator.

7.3 Data Quality Control

BIOTRONIK will review study data. At any time, reports may be generated on data completion and missing data for each study site. The EDC system will be used to track received and expected follow-up data and eCRFs for each participant. This

system provides the capability to monitor the status, volume, and disposition of data. In addition, study data will undergo automatic edit and plausibility checks which provide information to the study sites to help improve and maintain data quality control procedures designed to detect inaccuracies and inconsistencies.

To ensure protocol compliance at all participating study sites, BIOTRONIK monitors will conduct monitoring visits and/or centralized monitoring throughout the course of the study (refer to **Section 11**).

7.4 Subject Data Confidentiality

All information and data collected for the BIOFLOW-VII study concerning subjects or their participation in this investigation will be considered confidential by personnel at BIOTRONIK, BIOTRONIK's parent company, its subsidiaries and affiliates, as well as contracted designees, such as the CEC, Core Laboratory, EDC vendor and any other authorized third parties. Only authorized BIOTRONIK personnel or an authorized BIOTRONIK representative will have access to these confidential files. All data will be handled in accordance with applicable international, national and local laws, including the Health Insurance Portability and Accountability Act (HIPAA) of 1996. In order to verify the study data and ensure study integrity, monitors from BIOTRONIK, the FDA, other national regulatory and/or public health authorities and the reviewing IRB, if applicable, may review and/or copy the study records. Source documents supplied to the CEC or Core Laboratory will have confidential subject identifiers redacted. All data used in the analysis and reporting of this study will not include subject names or other identifiable references.

8 Protocol Compliance

The investigator is required to conduct this study in accordance with the signed Investigator Agreement and clinical protocol. The investigator shall notify BIOTRONIK and the reviewing IRB in writing no later than 5 working days after any significant deviation from the clinical protocol to protect the life or physical well-being of a subject in an emergency. Except in such emergency, prior approval by BIOTRONIK is required for significant deviations from the clinical protocol.

The site is responsible for reporting noncompliance via Protocol Noncompliance eCRFs. BIOTRONIK categorizes protocol noncompliance instances as either violations or deviations. Both protocol violations and deviations will be reported in the interim and final clinical progress reports to FDA.

BIOTRONIK will evaluate the noncompliance and issue corrective actions, as necessary, which may include but are not limited to, re-training, discontinuing enrollment at the study site, or closing the study site.

8.1 Protocol Violations

Protocol violations are defined as instances where the protocol requirements and/or regulatory guidelines were not followed and are generally more serious in nature than deviations. Protocol violations are considered to potentially affect the subject's rights, safety, or well-being, and/or the scientific soundness/data reliability, accuracy, or completeness of the primary study endpoint data.

Protocol violations include, but are not limited to:

- Failure to obtain consent or other instances in which the subject did not provide consent.
- Subject inclusion/exclusion violations.
- Protocol requirement violations that affect the primary endpoint of the study design.

8.2 Protocol Deviations

Protocol deviations are defined as instances where protocol requirements or regulatory guidelines were not followed but are generally less serious in nature than violations. Protocol deviations generally do not affect the subject's rights, safety, or well-being and/or the completeness, accuracy and reliability of the study primary endpoint data. Instances of noncompliance should be considered a deviation if it does not meet the criteria for being considered a violation.

Protocol deviations include, but are not limited to:

- Informed Consent documentation issues such as incomplete ICF, missing dates for signature(s), missing initials or illegible information, subject signature date completed by someone other than subject, utilization of an outdated or non-IRB approved ICF, incomplete associated forms required at time of consent, etc. This is not an exclusive list.

- Procedure not performed within the allowed timeframe.
- Required data not obtained.

8.3 IRB Reporting of Noncompliance

The investigator must notify the reviewing IRB of all noncompliance issues per the IRB and protocol reporting requirements. At a minimum, all violations and noncompliance issues related to informed consent and informed consent documentation should be reported to the IRB.

In some instances, such as failure to obtain consent, the investigator should also seek guidance from the IRB to ensure the subject received appropriate information to consider their participation in the study.

The site should provide a copy of the IRB protocol noncompliance notification (as applicable) to BIOTRONIK.

8.4 Follow-up Compliance

Sites are expected to ensure follow-up visit compliance over the duration of the study.

Although the study sample size has been calculated with a 10% subject attrition rate over the first year, subject retention in a 5 year study may pose additional, unforeseen challenges. The EDC system includes an overview of each subject's follow-up schedule, including the windows for each follow-up. BIOTRONIK will provide additional tools to the sites in an effort to minimize the number of subjects that are lost to follow-up.

In addition, BIOTRONIK monitors will review subjects, including those that may be lost to follow-up, to ensure protocol and study visit compliance.

8.5 Audits/Inspections

Study centers may be audited during the course of and after completion of the clinical study by BIOTRONIK or BIOTRONIK designees, the FDA, IRB, or other applicable regulatory authorities.

The investigator must provide the auditor with all clinical study documents including the medical records for all enrolled subjects.

9 Risk Analysis

This is a post-approval study conducted using legally marketed devices implanted according to their approved labeling. BIOTRONIK foresees no additional risks associated with this study beyond those stated in the IFU for the Orsiro stent. The only research related risk is the potential loss of confidentiality that is minimized by PHI redaction in the study.

10 Study Organization

10.1 Sponsor

BIOTRONIK as the study sponsor has the overall responsibility for the conduct of the study, including ensuring that the study meets and is conducted within the regulatory requirements specified by each reviewing regulatory authority. The sponsor, and/or other designees will ensure adherence to the sponsor general duties, selection of investigators, monitoring, supplemental applications, maintaining records and submitting reports.

BIOTRONIK's general duties include submitting the application to appropriate regulatory authorities and obtaining overall regulatory approval.

The sponsor or its designees are responsible for ensuring informed consent is obtained, proper clinical site monitoring is performed, providing quality data that satisfy regulations, and informing study investigators of deviations from the protocol, as appropriate.

BIOTRONIK or its designee will prepare written reports and a final report as directed.

10.2 Clinical Events Committee

A Clinical Events Committee (CEC) will be established consisting of independent physicians familiar with the treatment of coronary artery disease who are not participants in the study. The CEC will review and adjudicate all potential endpoint events reported by study sites. Source documents supplied to the CEC will have confidential subject identifiers and site identifiers redacted. To minimize bias, members will not participate as investigators.

The CEC is charged with the development of specific criteria used for the categorization of clinical events and clinical endpoints in the trial. Explicit rules outlining the minimum amount of data required, and the algorithm followed to classify study endpoint-related clinical events will be established. The CEC will review and adjudicate study endpoint-related clinical events in which the required minimum data are available. The committee will also review and rule on all deaths that occur throughout the trial.

10.3 Angiographic Core Laboratory

An Angiographic Core Laboratory (Core Lab) will independently assess repeat and/or unscheduled angiograms submitted by clinical sites for a suspected restenosis of a target vessel during the study follow-up period. The Core Lab will provide independent review of angiographic follow-up of the treated target lesion, quantitative target lesion characteristics, and quantitative study stent results, to support the evaluation by the CEC.

Sites should obtain angiographic images in accordance with standard of hospital practice but should make efforts to ensure the final stent location is documented at the initial index procedure and that any re-evaluation includes the study stent.

Initial index procedure, staged procedure (if applicable), and repeat procedure angiograms for all subjects will be kept on file at the study sites. If coronary angiograms are performed during the trial follow-up period due to suspicion of restenosis of the target vessel, a revascularization of the target vessel, stent thrombosis or in follow-up to a myocardial infarction, sites should submit both the index procedure and follow-up angiography to the Core Lab for analysis.

The Core Lab will provide sites with a written procedural manual describing the procedures for submitting angiograms. Submission documentation of images to the Core Lab (i.e. Core Lab submission worksheet), as well as, a copy of the images submitted (via CD/DVD), should also be kept on file at the site.

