3.1.6 Angiographic Exclusion Criteria

Subjects will be excluded from the trial if any of the target lesions/vessels met any of the following angiographic criteria during the index procedure:

1. Target lesion was located within or treated through a saphenous vein graft or arterial graft.

2. Target lesion was a restenotic lesion that was previously treated with a bare metal or drug-eluting stent (in-stent restenosis).
3. Target lesion had any of the following characteristics:
 - a. Lesion location is within the left main coronary artery, or within 3 mm of the origin of the left anterior descending (LAD) or left circumflex (LCX).
 - b. Involves a side branch of > 2.0 mm in diameter.

Note: Lesions within 3 mm of the origin of the right coronary artery may be treated.
4. Target vessel/lesion was excessively tortuous/angulated or is severely calcified, that would prevent complete inflation of an angioplasty balloon. This assessment should be based on visual estimation.
5. Target vessel had angiographic evidence of thrombus.
6. Target lesion was totally occluded (100% stenosis).
7. Target vessel was treated with brachytherapy any time prior to the index procedure.

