3.2 Study Procedures and Visits

Subjects will be followed for a period of 5 years post-index procedure.

Table 3 provides an overview of the study schedule including required visits and associated follow-up windows.

Table 3: Visit Assessment Schedule / Schedule of Events

	Index Procedure	Post-Procedure Enrollment Visit	1 Month ± 7 Days	1 Year ± 30 Days	2, 3, 4, 5 Years ±60 Days	Unsched. Visit
			Telephone Interview or Office Visit	Telephone Interview or Office Visit	Telephone Interview or Office Visit	
Informed consent form ¹		X ¹				
Demographics, clinical status, medical history, pre-procedure cardiac biomarkers (CK, CKMB or troponin), CBC, cardiovascular and antiplatelet/anticoagulant medications		X ²				
Index procedure information		X ³				
Post-procedure cardiac biomarkers (CK, CKMB or troponin)		X ⁴				
Ischemic/angina status		X	X	X	X	
12-lead ECG		X	X ⁵	X ⁵	X ⁵	
Angiography to assess lesion characteristics and final stent location	X ⁶					X ⁶
AEs and SAEs ⁷		X	X	X	X	X
Antiplatelet medical therapy		X	X	X	X	X

AE = adverse event; CBC = complete blood count; CK = creatine kinase; CKMB = creatine kinase myocardial band; ECG = electrocardiogram; SAE = serious adverse event

¹ Informed consent must be obtained after the index procedure. The date of index procedure is considered day 0 and informed consent (enrollment) can occur as late as 24 hours post-index procedure.

² Retrospective collection of pre-procedure information. Laboratory results (including cardiac biomarkers and CBC) collected only if testing performed per standard of care.

³ Retrospective collection of index procedure information.

⁴ Cardiac biomarkers collected only if testing performed per standard of care. It is anticipated that cardiac biomarker testing per standard of care generally would include subjects with positive cardiac biomarkers prior to the procedure, subjects with procedural complications and subjects with signs or symptoms of possible coronary ischemia post procedure.

⁵ ECG collected only if an office visit is performed and if ECG is performed per standard of care.

⁶ Images from standard of care angiography during index procedure should be retained and may be requested for submission to Angiographic Core Lab if subject undergoes a repeat angiogram. Angiographic data collected during any repeat procedure on the target vessel(s) must be made available to the Clinical Events Committee (CEC) and Angiographic Core Lab.

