3.3.4 Reporting of Unscheduled Evaluations

Subjects may present to the clinic outside of the scheduled follow-up windows. Such unscheduled study evaluation will be reported if the subject has experienced an AE.

Subjects assessed at an unscheduled study evaluation may require diagnostic testing (e.g. ECG, angiogram, CKMB or troponin levels) and/or a revascularization procedure to further evaluate and treat ischemic symptoms. Any repeat procedure must be reported on the relevant eCRFs, including any unscheduled evaluations prior to the repeat procedure and/or adverse events associated with the procedure, including separate AEs for each revascularization site if multiple sites were treated.

Any repeat or unscheduled diagnostic or interventional coronary revascularization procedure performed should include a diagnostic assessment of the target lesion(s) and study stent(s). Angiographic data collected during any repeat procedure on the target vessel(s) must be made available to the CEC for an independent review and assessment. Likewise, the angiographic images should be submitted to the Angiographic Core Laboratory for an independent review and assessment of the target lesion and study stent.

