5.2 Protocol Defined Reportable Adverse Events

The investigator shall report to the sponsor, by completing the appropriate eCRF, the following types of events experienced by the subject after enrollment (consent)*:

- All serious adverse events.
- All potential endpoint events, including death, MI, stent thrombosis, TLR, and TVR adverse events.
- All adverse events possibly related to the device and/or procedure.
- Abnormal laboratory findings will be considered AEs only if related to potential endpoint events (e.g., elevated cardiac biomarkers), or if determined by the investigator to be clinically significant.

***Note: Adverse events occurring since the beginning of the initial index procedure (prior to consent), will be collected retrospectively.**

Other than adverse events occurring since the beginning of the initial index procedure, pre-existing conditions (underlying conditions present prior to obtaining subject consent) that are clearly documented in the subject's medical record are not required to be reported as adverse events, unless there is an increase in severity or frequency or a change from the pre-enrollment baseline during the course of the study.

All complaints will be reported through the standard market release product reporting process.

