‡When the stented segment is in the left circumflex coronary artery or in the presence of preexisting electrocardiographic abnormalities (e.g., left bundle branch block, paced rhythms), definitive evidence of localization may be absent and Clinical Events Committee adjudication is based on review of all available evidence).

§Defined as the moment the patient is undraped and taken off the catheterization table.

TARGET LESION FAILURE (TLF)

Cardiac death, target vessel myocardial infarction (Q-wave or non-Q-wave), or clinically-driven target lesion revascularization.

TARGET LESION REVASCULARIZATION (TLR)

Repeat percutaneous intervention of the target lesion or bypass surgery of the target vessel performed for restenosis or other complication of target the lesion.

The target lesion is defined as the treated segment including the 5 mm margin proximal and distal to the stent.

See also *Clinically Driven Target Lesion Revascularization*.

TARGET VESSEL FAILURE (TVF)

Composite endpoint comprised of cardiac death, target vessel myocardial infarction or clinically-driven target vessel revascularization.

Target vessel failure will be reported when any of the following events occur:

- Recurrent MI occurs in territory not clearly attributed to a vessel other than target vessel.
- Cardiac death not clearly due to a non-target vessel endpoint.
- Target vessel revascularization is determined.

TARGET VESSEL MYOCARDIAL INFARCTION (MI)

Myocardial infarction that occurs in a territory that cannot be clearly attributed to a vessel other than the target vessel.

TARGET VESSEL REVASCULARIZATION (TVR)

Repeat percutaneous intervention or surgical bypass of any segment of the target vessel.

Target vessel is defined as the entire major coronary vessel proximal and distal to target lesion, including upstream and downstream branches and the target lesion itself.

See also *Clinically Driven Target Vessel Revascularization*.

THROMBOLYSIS IN MYOCARDIAL INFARCTION (TIMI) CLASSIFICATION²⁷

System developed during Thrombolysis in Myocardial Infarction (TIMI) trials for grading severity of stenosis and extent of blood flow through coronary arteries.

TIMI 0: No perfusion.

TIMI 1: Penetration with minimal perfusion. Contrast fails to opacify entire bed distal to stenosis for duration of cine run.

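### A repeat revascularization that the site codes as non-target vessel has no required route to the CEC or Core Lab, and errors through this gap can only lower TLF

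*Protocol*

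**What the plan says.** **How TLF is counted.** Protocol Section 2.1.1 and SAP Section 1.3 take the TLF rate from CEC-adjudicated events. Protocol Section 10.2 has the CEC review the potential endpoint events that sites report, plus all deaths. Section 5.2 describes these as "All potential endpoint events, including death, MI, stent thrombosis, TLR, and TVR adverse events".

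**Which films are sent.** Section 3.3.4 states: "Angiographic data collected during any repeat procedure on the target vessel(s) must be made available to the CEC for an independent review and assessment". Section 10.3 requires index and follow-up films at the Core Lab for an angiogram performed "due to suspicion of restenosis of the target vessel, a revascularization of the target vessel, stent thrombosis or in follow-up to a myocardial infarction". Footnote 6 to Table 3 (Section 3.2) adds that index images "may be requested for submission to Angiographic Core Lab if subject undergoes a repeat angiogram". That provision has no vessel condition, but it is optional.

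**What is recorded whatever the vessel.** Section 3.3.4 says "Any repeat procedure must be reported on the relevant eCRFs", "including separate AEs for each revascularization site if multiple sites were treated". Each follow-up visit also asks about any coronary intervention since the last contact (Sections 3.3.1 to 3.3.3).

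**How target status is defined.** The Section 17 glossary counts the whole major vessel with its upstream and downstream branches as target vessel and places the ramus with the circumflex. Under TLR it says: "The target lesion is defined as the treated segment including the 5 mm margin proximal and distal to the stent". The glossary entry for coronary artery names the LAD, circumflex and right coronary territories but does not assign the left main.

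**The concern.** For a repeat revascularization with no MI, no stent thrombosis and no suspicion of target-vessel restenosis, each mandatory trigger turns on whether the procedure was on the target vessel. The site makes that call, and in a single-arm study the site knows which stent is in place. If it records another vessel, the event is in EDC but nothing stated moves it to the CEC or the Core Lab.

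The definitions leave room for honest error: a procedure on the ramus or a side branch, or on the left main near a proximal LAD or circumflex stent. MI has a conservative default, since it counts as target vessel unless clearly attributable elsewhere. Revascularization has no such default.

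The two kinds of error are treated differently. A non-target procedure wrongly coded as TLR or TVR reaches the CEC and can be corrected. A TLR or TVR wrongly coded as non-target has no required route there. What slips through can therefore only reduce TLF and TVF. With a fixed 6.9% goal and no control arm to carry the same error, that favours passing.

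**Working it through.** **1. Routes to review, by how the site codes the procedure**

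| Site record of the repeat revascularization | Required route to CEC or Core Lab? |
|---|---|
| TLR | Yes (3.3.4, 5.2, 10.3) |
| TVR but not TLR | Yes; the CEC can upgrade it to TLR |
| Non-target, with stent thrombosis or in follow-up to an MI | Yes; these triggers in 10.3 are not worded by vessel |
| Non-target, but target-vessel restenosis suspected | Yes (10.3) |
| Non-target, none of the above | None stated; EDC record only |

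The gap is the last row.

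**2. The left main example.** Section 3.1.6 excludes lesions within 3 mm of the LAD or circumflex origin, so a lesion starting just beyond 3 mm is eligible. If the stent begins at the lesion edge (assumption), the 5 mm margin runs just under 5 − 3 = 2 mm past the origin into the left main. A later left main PCI at that point falls within the target lesion as defined, yet a site could record it as another vessel.

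**3. The plan's own sample size.** Inputs from Protocol Section 4.2.1: goal 6.9%, expected rate 4.0%, one-sided 0.025, power 80%. The exact test is from Section 4.3.3. The pass limit c is the largest count with P(X ≤ c | n, 0.069) ≤ 0.025, and power is P(X ≤ c | n, 0.04).

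- n = 495: c = 23, type I error 0.0245, power 80.5%. This is the smallest n that reaches 80%, so the plan's 495 reproduces.
- Enrolment: 500 / 0.90 = 555.6, rounded up to 556. This also reproduces.
- n = 500: pass at 23 or fewer events (4.6%), type I error 0.0214, power 79.2%. At 24 events p = 0.034 and the test fails.

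**4. Effect of unadjudicated events.** Let q be the share of true TLFs that are TLR alone, and m the fraction of those coded as non-target and never reviewed. The counted rate at the goal is 0.069 × (1 − q·m), and the false-pass rate is P(X ≤ 23 | 500, that rate). The documents give neither q nor m; both are assumptions.

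| q | m | TLFs lost (q·m) | Counted rate at the goal | False-pass rate | Events lost of 20 (500 × 4.0%) |
|---|---|---|---|---|---|
| – | 0 | 0 | 6.90% | 2.1% | 0 |
| 30% | 2% | 0.6% | 6.86% | 2.3% | 0.12 |
| 30% | 5% | 1.5% | 6.80% | 2.6% | 0.3 |
| 30% | 10% | 3.0% | 6.69% | 3.2% | 0.6 |
| 50% | 2% | 1.0% | 6.83% | 2.5% | 0.2 |
| 50% | 5% | 2.5% | 6.73% | 3.0% | 0.5 |
| 50% | 10% | 5.0% | 6.56% | 4.2% | 1.0 |

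The false-pass rate crosses 0.025 when about 1.1% of true TLFs are lost.

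**The case against.** Much of the case on the other side stands.

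- **More than one trigger.** A reader might infer that review happens only if the site codes the target vessel. Section 10.3 does not support that: stent thrombosis and MI follow-up carry no vessel condition, and suspicion of target-vessel restenosis is enough by itself.
- **Upgrades are possible.** A reader might also infer that adjudication can only remove TLRs. It can add them: site-coded TVRs are reviewed, so errors within the same vessel, including those about the 5 mm margin, are covered.
- **Other safeguards.** Any repeat procedure should image the target lesion and study stent (3.3.4). All SAEs are reportable (5.2), copies of supporting documents come with each event form (5.3.1), adverse events may be verified centrally (11.1), and films are kept on file (10.3). These make a miscoded case detectable, but no step requires anyone to look for one.
- **Few places to hide.** PCI planned within a year and untreated significant stenoses are exclusions (3.1.4), which should limit early non-target procedures.
- **The Charter.** SAP Section 1.3 defers to CEC Charter definitions, Protocol Section 10.2 promises explicit classification rules, and the list in 5.2 is not shown to be exhaustive. A wider trigger may already exist.
- **Size.** One lost event changes the result only if the true count is exactly 24.

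These points narrow the gap. They do not supply a stated route for an isolated revascularization coded as non-target.

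**Conclusion.** The point holds in a limited form. As written, the protocol leaves one class of event without required adjudication: a TLR or TVR coded as non-target vessel, with no MI, stent thrombosis or suspected target-vessel restenosis. Errors there act in one direction, towards meeting the goal.

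A reader might go further and conclude that TLF is biased low. The documents do not show that, because they give no miscoding rate. Nor do they support a large TLR share. BIOFLOW-V clinically-driven TLR of 2.6% at 2 years less 0.7% between years 1 and 2 (Section 15), over a SCAI-based 1-year TLF of 2.6%, gives 1.9 / 2.6 = 73%. That figure subtracts a landmark rate from a cumulative one and ignores overlap with MI and cardiac death, and TLRs with MI already have a route to review.

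On the assumed ranges (TLR-only share 30-50%, miscoding 2-10%), the false-pass rate is about 2.3-4.2% against 2.1% with no loss, and at most one event in an expected 20 goes uncounted. The true effect may be smaller, and may be nil if the CEC Charter already requires vessel-neutral review.

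**What to change.** - **Section 5.2:** add any coronary revascularization after the index procedure to the potential endpoint events, so that the CEC, not the site, assigns TLR, TVR or non-target from the procedure report.
- **Sections 3.3.4 and 10.3:** require index and repeat images to go to the Core Lab and the CEC whenever the treated segment shares a coronary territory with a study stent (including left main, ramus and branches), or when the report cannot exclude this.
- **Events already in EDC:** apply the same rule to revascularizations recorded so far.
- **CEC Charter:** if it already sets this trigger, cite the rule in the protocol instead.

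The cost is wording in three sections and a modest number of extra report and film submissions to a CEC and Core Lab that already exist. No visit or procedure is added. Some of the collection would be retrospective, because the SAP (May 2022) describes the 25%, 50% and 75% enrolment comparisons as complete. The sites would have to make the submissions, since Section 10.4 bars sponsor personnel from requesting or retrieving subject medical records. The TLF rate may turn out slightly less favourable.
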